10.1 Adverse Events and Reporting

Oversight of the pilot will be the responsibility of the pilot PI: [name], DPhil. [name] and study investigators will meet on a regular basis throughout the study period and will be in direct contact with the clinical study nurse conducting the intervention to obtain ongoing feedback. In addition, the protocol will undergo Institutional Review Board (IRB) evaluation.

De-identified study data will be accessible at all times for the BWH pilot PI and coinvestigators to review, if applicable. The study team will also ensure that all protocol deviations for the pilot study are reported to the NIH and the IRB according to the applicable regulatory requirements. Compliance of regulatory documents and study data accuracy and completeness will be maintained through an internal study team quality assurance process.

Definition:

Adverse Event (AE): Any untoward or unfavorable medical occurrence in a human study participant, including any abnormal sign (e.g., abnormal physical exam or laboratory finding), symptom, or disease, temporally associated with the participants' involvement in the research, whether or not considered related to participation in the research.

Adverse Events will be classified using the following rating scales:

- Severity: Mild, Moderate or Severe
 - Mild: Awareness of signs or symptoms but are easily tolerated
 - Moderate: Events introduce a low level of inconvenience or concern but may interfere with daily activities but are usually improved by simple therapeutic measures.
 - Severe: Events interrupt the participants' normal daily activities and generally require systemic drug therapy
- Expectedness: Unexpected or Expected
 - Unexpected: nature or severity of the event is not consistent with the condition under study.
 - Expected: event is known to be associated with the intervention or condition under study

Serious Adverse Event (SAE): Any adverse event that:

- Results in death
- Is life threatening, or places the participant at immediate risk of death from the event as it occurred
- Requires or prolongs hospitalization
- Causes persistent or significant disability or incapacity
- Results in congenital anomalies or birth defects
- Is another condition which investigators judge to represent significant hazards

Given the minimal risk nature of the study, in which the intervention involves enhanced education and monitoring of hypertension for patients at MGB, the PI does not expect any SAEs or AEs related to the information delivered in this trial.

Reporting:

As previously described, no SAEs or AEs are expected as part of this study, as the study team will not be providing any direct care to patients other than educational counseling received by a trained study nurse. All medical decisions will ultimately be made by the patient's medical team at MGB.

However, if the study team receives communication from MGB leadership or participants themselves and thus become aware of any AEs or SAEs throughout the course of the study, they will collect this information. Any reports of deaths will be submitted to the NIA Program Officer and to the Safety Officer (SO) within 24 hours. Any unexpected SAEs will be reported to the NIA PO, SO and the IRB within 48 hours of the study's knowledge of the SAE. All other reported SAEs and AEs received by the study team will be reported to the NIA Program Officer and to the SO quarterly.

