6.2 Between Study Visits

Upon enrollment of the patient-subject and their network members in the **Social Networks arm**, study staff will use an MGB-approved and properly configured study-specific cellular device to initiate a group SMS thread containing the index patient-subject, their consented network members (if applicable), and their assigned RA/study staff. This group SMS thread will be utilized for three types of communication: 1) appointment reminders from study staff, 2) facts/tips related to blood pressure control from study staff, and 3) organic correspondence between the patient and network members. Correspondence from study staff will be scripted (see "*Text message list*" attachment). Study staff will also collect email addresses from patients at baseline to use for back-up communication. Patients will be read the following MGB-required warning language regarding unsecure email by study staff: *"The Mass General Brigham standard is to send email securely. This requires you to initially set up and activate an account with a password. You can then use the password to access secure emails sent to you from Mass General Brigham. If you prefer, we can send you "unencrypted" email that is not secure and could result in the unauthorized use or disclosure of your information. If you want to receive communications by unencrypted email despite these risks, Mass General Brigham will not be held responsible. Your preference to receive unencrypted email will apply to emails sent from this research group/study only."* The study staff will then obtain verbal permission to send unencrypted email and document within REDCap prior to sending any unsecure email. If necessary, study staff will follow up with patients over secure or unsecure email (per their preference) using the subject line "Follow-up for TEAMS-BP Study" if they are unable to make contact with the patient by phone after they are discharged from the hospital. All secure email communication will be sent using the SEND SECURE encryption mechanism and communication will resume on the cellular device if possible once contact has been made.

Upon enrollment of patient-subjects in the **Individual Counseling arm**, study staff will use an MGB-approved and properly configured study-specific cellular device to initiate an SMS thread with the

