patient-subject. This SMS thread will be utilized for two types of communication: 1) appointment reminders and 2) facts/tips related to blood pressure control from study staff. Correspondence from study staff will be scripted (see “Text message list” attachment). Study staff will also collect email addresses from patients at baseline to use for back-up communication. Patients will be read the following MGB-required warning language regarding unsecure email by study staff: *“The Mass General Brigham standard is to send email securely. This requires you to initially set up and activate an account with a password. You can then use the password to access secure emails sent to you from Mass General Brigham. If you prefer, we can send you “unencrypted” email that is not secure and could result in the unauthorized use or disclosure of your information. If you want to receive communications by unencrypted email despite these risks, Mass General Brigham will not be held responsible. Your preference to receive unencrypted email will apply to emails sent from this research group/study only.”* The study staff will then obtain verbal permission to send unencrypted email and document within REDCap prior to sending any unsecure email. If necessary, study staff will follow up with patients over secure or unsecure email (per their preference) using the subject line “Follow-up for TEAMS-BP Study” if they are unable to make contact with the patient by phone after they are discharged from the hospital. All secure email communication will be sent using the SEND SECURE encryption mechanism and communication will resume on the cellular device if possible once contact has been made.

Upon initiation of the group SMS thread, study staff will send a text message with the date, time and Zoom meeting link for the first session based on the time agreed upon with the patient during the enrollment visit.

Text messages will only be read during regular business hours (Monday through Friday, 9AM – 5PM Eastern Time). Texts sent on nights, weekends or holidays will not be read until the following business day. If any participant sends a text message prompting a response to the study staff, the staff will respond utilizing minimum necessary MGB principles. For the following participant responses, automatic action will be taken with messages as follows:

Patient Response	Automated action or text back to patient
Stop	<Stop text messages>
Quit	<Stop text messages>

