6.3 Counseling Sessions

All counseling sessions will take place remotely through Zoom, an MGB-approved secure video platform. In both the individual counseling and social network arm, participants will meet with the study nurse with an RA present on weeks 2,6, and 12 (+/- 7 days).

6.3a Counseling Session 1—On Week 2 (+/- 7 days)

The first counseling session will take place two weeks after initial enrollment. Study staff will ensure that only participants who have completed the consent process join the Zoom meeting.

Individual Counseling Arm

Patients in the individual counseling arm will meet individually with the study nurse. The nurse will provide counseling on the basics of blood pressure, taking and adjusting medications, monitoring blood pressure, reducing salt, and being physically active. The patients will then schedule their next session and collect a blood pressure measurement with cuff provided by the study staff under direct supervision by the nurse.

Social Network Arm

At the beginning of this session, the Research Assistant/study staff will confirm that all network-participants have completed the electronic consent process via REDCap.

The study nurse will begin the team-based counseling session in which she will provide counseling on teamwork and the same blood pressure control topics covered with the individual counseling group. The teamwork specific topics will include how networks can work together as a team, communication tips for engaging with one another and spreading positive messages and establishing the roles and responsibilities of each network team member. The team will schedule the following session and the patient will collect a blood pressure measurement with the cuff provided by the study staff under direct supervision by the nurse.

6.3b Counseling Session 2—On Week 6 (+/- 7 days)

The second counseling session will take place six weeks after initial enrollment. Participants in both arms will have received text messages every week in the three weeks between session 1 and session 2. Study staff will ensure that only participants who have completed the consent process join the Zoom meeting.

Individual Counseling Arm

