6.5 Data Collection Schedule

Time point	Individual Counseling Arm	Social Network Arm
Baseline (Week 0)	
Written consentPERSNETDemographics and stroke data (Age, Sex, Stroke severity, Charlston comorbidity index)Blood pressure measure under direct observation	
Written consentPERSNETDemographics and stroke data (Age, Sex, Stroke severity, Charlston comorbidity index)Blood pressure measure under direct observationNetwork members contact info
Session 1 (Week 2 (+/- 7 days))	
BP measure under direct observationFeasibility measures: number of participants, time of session, connection problems.	
BP measure under direct observationFeasibility measures: number of participants, time of session, connection problems.
Session 2 (Week 6 (+/- 7 days))	
BP measure under direct observationFeasibility measures: number of participants, time of session, connection problems.	
BP measure under direct observationFeasibility measures: number of participants, time of session, connection problems.
End line (Week 12 (+/- 7 days))	
BP measure under direct observationPERSNETPROMISFeasibility measures: number of participants, time of session, connection problems.	
BP measure under direct observationPERSNETPROMISCaregiver burden (primary caregiver)Intervention process evaluation (qualitative semi-structured interview)Feasibility measures: number of participants, time of session, connection problems.
Upon completion of study (or after withdrawal)	
Implementation survey or qualitative interview	
Implementation survey or qualitative interview

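### Adverse events are collected passively, with no scheduled question in either arm and extra reporting routes in the network arm, so counts may be incomplete and any by-arm table open to ascertainment bias

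*Combined protocol and SAP*

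**What the plan says.** Section 10.1 of the combined protocol and SAP defines an adverse event as any untoward medical occurrence in a participant, "whether or not considered related to participation in the research". It then states that "no SAEs or AEs are expected as part of this study", because the team gives no care beyond educational counseling. Collection follows "if the study team receives communication from MGB leadership or participants themselves and thus become aware of any AEs or SAEs". Deaths go to the funder's program officer and the safety officer within 24 hours. Unexpected serious events are reported within 48 hours of the study learning of them, and the rest quarterly.

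Section 6.3 gives both arms the same three nurse sessions, at weeks 2, 6 and 12. The stated counseling topics are "taking and adjusting medications, monitoring blood pressure, reducing salt, and being physically active", plus teamwork in the network arm. At each session the Section 6.5 Data Collection Schedule lists an observed blood pressure and "Feasibility measures: number of participants, time of session, connection problems". Week 12 adds questionnaires and, in the network arm only, a caregiver scale and an interview.

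Section 6.2 gives the network arm a "group SMS thread containing the index patient-subject, their consented network members (if applicable), and their assigned RA/study staff". For the control arm it says: "This SMS thread will be utilized for two types of communication: 1) appointment reminders and 2) facts/tips related to blood pressure control from study staff".

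**The concern.** The definition is broad, but the collection rule depends on news reaching the team. Patients enter within 14 days of an ischemic stroke, with an NIHSS of up to 21, and are followed for 12 weeks. Unrelated events are foreseeable, and the plan's own definition counts them. Staff see every patient three times, yet no enquiry about events is scheduled.

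The people who can bring news also differ by arm. If a network-arm patient is hospitalized or dies, a relative in the group thread can tell staff. In the control arm no relative is enrolled, and the patient may be unable to write. These are the events with the shortest reporting deadlines, and the reporting duty starts only once staff know.

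At stake is the quality of the information on which the safety officer advises (Sections 10.2 and 10.3), and of any adverse event table published with the pilot.

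**Working it through.** **The plan's own figures.** The documents give no adverse event rate, detection rate or by-arm event count, so there is no figure on this point to reproduce. The one computed design figure, 27 per arm in Section 9.2, does reproduce: 2 × (1.96 + 0.84)² × 13² / 10² = 26.5, rounded up to 27. It is not in dispute, and the fix leaves it unchanged.

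**Routes by which an event can reach staff**

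| Route | Individual counseling arm | Social network arm |
|---|---|---|
| Sessions at weeks 2, 6, 12 (Sections 3, 6.3, 6.4) | Nurse, research assistant, patient | The same, plus network members |
| Text thread (6.2) | Patient and staff; reminders and tips | Patient, members and staff; also free exchange between patient and members |
| Week 12 semi-structured interview (6.4) | None | Patient and members |
| Contact with clinical leadership (10.1 to 10.3) | Available | Available |
| Scheduled event question (6.5 Data Collection Schedule) | None listed | None listed |
| Record search for events (6.1 uses the record for covariates and discharge blood pressure) | None described | None described |

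Sections 4.2b and 6.3a call network members participants, so the Section 10.1 trigger takes in their reports. For a text needing medical attention, Section 6.2 specifies an automatic referral message and no step for logging an event.

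**Illustration of size.** Inputs: n = 30 per arm (Section 6.6); true risk p, assumed equal in both arms; and detection probabilities d_C (control) and d_N (network), assumed.

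- Expected recorded patients with an event, per arm = n × p × d
- Recorded risk ratio = (n p d_N) / (n p d_C) = d_N / d_C, whatever n and p are
- Expected missed, both arms = n × p × (2 − d_C − d_N)

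With p = 20%, there are 30 × 0.20 = 6 true cases per arm:

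| d_C / d_N | Recorded, control | Recorded, network | Recorded ratio | Missed, both arms |
|---|---|---|---|---|
| 50% / 50% | 3.0 | 3.0 | 1.00 | 6.0 |
| 50% / 70% | 3.0 | 4.2 | 1.40 | 4.8 |
| 50% / 90% | 3.0 | 5.4 | 1.80 | 3.6 |
| 70% / 90% | 4.2 | 5.4 | 1.29 | 2.4 |
| 90% / 90% | 5.4 | 5.4 | 1.00 | 1.2 |

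For p from 10% to 30% the ratios do not change. Across the three unequal rows, the expected number missed then runs from 1.2 (30 × 0.10 × 0.40) to 7.2 (30 × 0.30 × 0.80). If detection were instead lower in the network arm by the same margins, the ratios would be the reciprocals: 1/1.29 = 0.78 to 1/1.80 = 0.56. Incompleteness and imbalance are separate faults: the 50%/50% row is unbiased as a ratio but misses half the cases.

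**The case against.** The strongest reply is that capture is not purely passive. Investigators are in direct contact with the study nurse (10.1) and in regular contact with clinical leadership (10.2, 10.3), and they plan to contact people who withdraw (6.5 Implementation evaluation). All of this is started by the team and none is confined to one arm. That stands, but it is general feedback, not systematic case finding.

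Second, Section 10.2 points to an Appendix A and to a manual containing the safety monitoring plan. Neither was available to check, and they may prescribe active collection. A reader might infer that staff never ask about events. The documents support only that no scheduled question is described.

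Third, a reader might infer that the arms cannot be compared on safety and that the trial's comparison suffers. Section 9.3 plans no between-arm adverse event analysis, Section 10.3 does not say that safety reports are split by arm, and a pilot of 60 would give few events even with perfect detection. That stands.

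Fourth, a reader might expect a spurious excess in the network arm. Extra reporters could raise detection there, but patients may also disclose less in front of relatives. Scheduled staff contact is the same in both arms, and control patients have their own thread with staff. Neither direction nor size is known.

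Finally, the statement that no events are expected may look like a contradiction of the broad definition. It refers back to a sentence limited to events related to the information delivered, and the plan does set reporting deadlines, so it is not a denial that stroke patients have events.

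**Conclusion.** The point holds in a limited form. As written, Section 10.1 relies on events being brought to the team, the visit schedule contains no event item, and the opportunity to report is wider in the network arm. Adverse event counts may therefore be incomplete, and any descriptive tabulation by arm would be open to ascertainment bias. It is an inference too far to say that events will certainly be missed or that an excess in a given arm will appear.

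The ratios of about 1.3 to 1.8 rest wholly on assumed detection probabilities with the network arm higher. They restate the ratio of those probabilities and are not an estimate for this trial. The conclusion also assumes that Appendix A and the manual do not already provide for active enquiry. The effect is confined to safety oversight and descriptive safety reporting; the primary systolic blood pressure analysis and the sample size are untouched. It is worth acting on because the remedy is cheap.

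**What to change.** Add one item to the Section 6.5 Data Collection Schedule and to Section 10.1. At weeks 2, 6 and 12 the nurse or research assistant asks every index patient, in both arms, the same short scripted questions on events since last contact: hospital visits, falls, new stroke symptoms, and anything else. Ask them without network members present, for example before members are admitted to the call. For a missed session, make the same follow-up attempt in both arms. Enter the answers in REDCap with the source of each report, and tabulate solicited events separately from volunteered ones for the safety officer. If Appendix A or the manual already provides this, a cross-reference in Section 10.1 is enough.

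The cost is one REDCap form and roughly two to three minutes per session. That is not negligible against the 10-minute exit assessment in Section 9.3 (2/10 to 3/10, or 20-30%). More unrelated events will be logged and will enter the quarterly reports. No extra visits or patients are needed.

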10.2 Planned Safety Monitoring

General oversight of this project by the Brigham and Women's Hospital (BWH) pilot PI ([name]) will occur throughout the study period, including regular contact with MGB clinical leadership involved in the project to obtain ongoing feedback. In addition, this protocol will undergo Institutional Review Board (IRB) evaluation. [name] (co-investigator) has previously overseen numerous pragmatic trials.

This study will include safety monitoring from an independent safety officer (SO) to perform data and safety monitoring activities (**see Appendix A**). This SO will advise NIA Program staff and the PI regarding participant safety, study risks and benefits, scientific integrity, participant recruitment, and ethical conduct of the study.

Therefore, the pilot PI will appoint a designed individual with relevant study and disease-specific expertise to serve as SO, submitted to the NIA PO for approval. Following approval, the SO will receive a manual of operating procedures containing the study protocol and DSMP prior to study enrollment. The PI has nominated [name], as the independent Safety Officer (SO), pending approval by the NIA PO, to act in an advisory capacity to the NIA PO and to evaluate the progress of the study.

10.3 Frequency of Monitoring

De-identified study data will be accessible at all times for the BWH pilot PI ([name]) and co-investigators to review, if applicable. The study team will also ensure that all protocol deviations for the trials are reported to the NIH and the IRB according to the applicable regulatory requirements. [name] will also be in routine contact with other MGB clinical leadership to obtain any feedback from clinicians or patients regarding the study. Compliance of regulatory documents and study data accuracy and completeness will be maintained through an internal study team quality assurance process. Safety reports are sent to the SO at least twice a year and will include a detailed analysis of study progress, data and safety issues.

11. Privacy and Confidentiality

- Study procedures will be conducted in a private setting

- Only data and/or specimens necessary for the conduct of the study will be collected
- Data collected (paper and/or electronic) will be maintained in a secure location with appropriate protections such as password protection, encryption, physical security measures (locked files/areas)
- Specimens collected will be maintained in a secure location with appropriate protections (e.g. locked storage spaces, laboratory areas) – N/A
- Data and specimens will only be shared with individuals who are members of the IRB-approved research team or approved for sharing as described in this IRB protocol
- Data and/or specimens requiring transportation from one location or electronic space to another will be transported only in a secure manner (e.g. encrypted files, password protection, using chain-of-custody procedures, etc.)
- All electronic communication with participants will comply with Mass General Brigham secure communication policies
- Identifiers will be coded or removed as soon as feasible and access to files linking identifiers with coded data or specimens will be limited to the minimal necessary members of the research team required to conduct the research
- All staff are trained on and will follow the Mass General Brigham policies and procedures for maintaining appropriate confidentiality of research data and specimens
- The PI will ensure that all staff implement and follow any Research Information Service Office (RISO) requirements for this research
- Additional privacy and/or confidentiality protections

Data for the study will be safeguarded by state-of-the-art security protocols. The facilities have 24-hour security and are protected by locked entrances. MGB has computer networks in place that employ up to date virus protection software and enable password protected access only to study investigators. The setup for analysis of these data will be the same as all the other IRB applications that the MGB research division submits for secondary use of data. All the datasets, including limited protected health information (PHI), will be stored only on secure servers at MGB's data center and will only be accessed by a limited number of individuals in the study team from this division who are all trained in data security and patient privacy.

To ensure the confidentiality and security of all data, the research team operates a secure, state-of-the-art computing facility housed at MGB's data center. The MGB data center is a secure facility that houses both computing environments as well as clinical systems and electronic medical records for several large hospitals in Eastern Massachusetts. Entry into the computer room requires staffed computer room security. The Division of Pharmacoepidemiology's computers are connected to the MGB networking backbone with 10 gigabit-per-second fiber links. Network security is overseen by electronic medical records systems to the research team's data. All data are transmitted to programmers' workstations in an encrypted state. Backups are created using 256-bit AES encryption, the current Department of Defense standard for data security, and are stored in a locked facility. The redundancy, extensive data power, and security of the computer facility confirm the capacity to collect and manage data and ensure confidentiality for all project participants.

The study team will also safeguard any identifiable information from the physicians in accordance with IRB practices, limit access to any information in accordance with IRB practices, limit access to the information to study investigators actively involved in the research who have all undergone human subjects research training.

All members of the research team have completed or will complete appropriate human subjects research training and patient privacy training related to the Health Insurance Portability and Accountability Act (HIPAA).

12. References

